The PI will review AEs and notify the IRB of any changes needed to the protocol. The IRB will be notified within 24 hours of any SAE (grade 4 or 5) occurring at this site via their online system for reporting SAEs, and additional information will be forwarded to the IRB as it becomes available. AE's (grades 2-3) will be reported by the PI to the IRB within 10 working days. Mild AE's (grade 1) will be reported at the annual continuing review. In addition, all laboratory values outside of the normal range will be discussed with the study participant, and appropriate arrangements will be made for treatment, if necessary. The annual summary of all adverse events and any audit reports will be sent to the IRB at the time of continuing review.

If the data received during the course of the study on a study participant indicate they he or she may benefit from (other) medical intervention, then the appropriate recommendation(s) and/or consultation(s) will be made.

A Data and Safety Monitoring Board, chaired by [name] MD (Professor of Medicine), and including [name] (Associate Professor of Medicine) will meet every 12 months with the PI, Co-Investigators, and the study research coordinator, to review study data, discuss any safety issues, and ensure compliance with the protocol.

Study Withdrawal/Discontinuation

Participants are free to withdraw at any time. Female participants who become pregnant will be removed from the study. If the participant's doctor decides that staying in the study places the participant at risk, she/he will be withdrawn. Any condition deemed by the study personnel to interfere with the participant's ability to complete the study will be cause for withdrawal. Subjects will be removed from study if they no longer meet the study criteria, if an SAE occurs, if they do not show up to study visits, or if the study is terminated.

Subjects that are removed or withdraw from the study will initiate the drug step-down protocol by decreasing their drug dose by 1000 mg for one week prior to stopping the drug completely.

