The effect of Vigabatrin on Insulin Sensitivity

NCT04321395

Principal Investigator:

[name]
Washington University School of Medicine in St. Louis, Missouri

Version 7
December 15, 2022

SPECIFIC AIMS

Nonalcoholic fatty liver disease (NAFLD) is a common complication of obesity and is associated with hyperinsulinemia, multi-organ insulin resistance and an increased risk of developing type 2 diabetes (T2D). The hallmark feature of NAFLD is an increase in intrahepatic triglyceride (IHTG) content. Data from studies conducted in rodent models suggest increased IHTG content can cause insulin resistance through signaling by the hepatic vagal afferent nerve (HVAN). In rodent models of obesity and NAFLD, HVAN activity is reduced leading to impaired insulin sensitivity and glucose control. The reduction in HVAN activity is likely due to increased hepatic release of GABA, an inhibitory neurotransmitter, attributable to increased expression of GABA-Transaminase (GABA-T). In lean rodents GABA-T acts to break down high levels of GABA to produce succinate semialdehyde and glutamate, but in the livers of obese mice, the opposite reaction occurs with increased succinate semialdehyde and glutamate availability driving the GABA-T reaction toward GABA production, rather than breakdown. Pharmacological inhibition of GABA-T in obese mice by treatment with vigabatrin, an irreversible inhibitor of GABA-T that is approved by the FDA to treat seizure disorders, improves glucose tolerance and reduces hyperinsulinemia, hyperglycemia, and insulin resistance. It is not known if vigabatrin can also improve metabolic function in people.

The overall goals of this pilot study are to determine the potential effect of vigabatrin on insulin sensitivity, insulin secretion and glycemic control in people with obesity and NAFLD (IHTG content $\geq 5.6\%$). Accordingly, we will conduct a 3-week, single-arm trial to assess the effect size of treatment with vigabatrin on the following specific aims with the larger goal of determining whether a large, randomized controlled trial investigating the effect of vigabatrin is warranted:

Aim 1: Determine the effect of GABA-T inhibition on insulin sensitivity in people with NAFLD. We will perform hyperinsulinemic-euglycemic clamp procedures plus stable isotope tracer infusions to assess skeletal muscle insulin sensitivity before and after treatment.

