The testing schedule presented in Table 1. All participants will undergo comprehensive outpatient screening visits, including medical examination, visual field examination, blood tests, EKG, and an MRI scan to assess IHTG content to determine eligibility for the study. Participants who meet the inclusion criteria will be admitted to the inpatient Clinical and Translational Research Unit (CTRU) at Washington University School of Medicine on two separate occasions to complete baseline testing. After completion of baseline testing, subjects will receive vigabatrin to be taken over 30 days. Participants will be instructed to take one 500 mg pill 2X/day for the first 7 days (days 0-6; 1000 mg/day), one pill in the morning and two pills in the evening for days 7-13 (1500 mg/day), and two pills twice a day for days 14-23 (2000 mg/day). On day ~21, participants will again arrive at CTRU an overnight fast for a repeat modified oral glucose tolerance test (mOGTT) with a hyperinsulinemic-euglycemic clamp (HEC) procedure and repeat peripheral vision tests performed on day ~23. Throughout the study, participants and the study team will be blinded to treatments. After completing the HEC, participants will begin stepping down the vigabatrin dose as recommended by the manufacturer, moving to the 1 pill 2X/day dose for days 24-30 before discontinuing treatment. Lastly, participants will be seen for repeat vision testing that occurred in screening approximately 6 months after initiation (5 months after discontinuation) of the drug.

Screening Visits

After informed consent is obtained, participants will undergo three separate screening visits to confirm eligibility.

Screening visit 1. Participants will arrive in the CTRU in the morning after they have fasted for 10h-12h overnight at home where they will undergo a comprehensive screening process, including a medical history, physical examination, standard blood tests and questionnaires to assess alcohol intake, eating habits, sleeping patterns, current level of anxiety, depression (measured with the Beck Depression Inventory-II³⁰), quality of life and any potential barriers that could interfere with their ability to complete all study requirements/visits.

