Vigabatrin capsules will be taken by participants daily for 30 days. Drug tablets will be administered orally as provided by the manufacturer and dosage matching the FDA label. Specifically, we will provide each patient with a total dosage of 44.5 g vigabatrin. Subjects will be instructed to take one 500 mg pill 2X/day for the first 7 days (days 0-6; 1000 mg/day), 1 pill in the morning and 2 pills in the evening for days 7-13 (1500 mg/day), and two pills 2X/day for days 14-23 (2000 mg/day). On day 24, participants will initiate a step-down protocol as recommended by the manufacturer, moving to the one pill 2X/day dose for days 24-30, before discontinuing treatment. Study participants will meet with the research coordinator or one of the investigators weekly to ensure compliance with the study protocol and problem-solve any barriers. Regular medical monitoring by the study research coordinator and medical staff will be performed during the entire study period. Subjects will be asked to come in weekly while on the drug. At the visit, a general wellness check (including depression screening with the Beck Depression Inventory-II³⁰), vital signs and body weight and a urine drug test will be obtained, and blood samples (7 ml of blood (~0.5 tablespoon)) will be obtained at the weekly visit for the first two weeks of dose escalation to assess routine laboratory tests. Study participants will be instructed to keep their body weight stable (< 2% change) during the treatment period.

Dispensing and accountability

A medication accountability log will be used to document dispensing of the vigabatrin to the participant and the return of unused product by the participant. The medication accountability log will document the participant ID, initials, the amount of medication and the date the drug was dispensed to the participant, and the amount of medication that the study participant returned. Participants will be instructed to return unused medications at every scheduled study visit and study end. The study research coordinator will perform a pill count and document this in the medication accountability log at each study visit.

Repeat studies

The HEC procedure and mOGTT performed at baseline as well as the MRI to determine liver triglyceride content at screening will be repeated after 3 weeks of treatment. In addition, depression measured with the Beck Depression Inventory-II³⁰ (measured at screening) will be re-assessed at the repeat mOGTT.

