Vision testing will be repeated during the clamp visit (day 23). Vision and depression (Beck Depression Inventory-II³⁰) will be assessed approximately 6 months after participants initiated the drug.

Table 1. Schedule of tests performed

Assessment	SCREENING			BASELINE TESTING		WEEK 3 TESTING		STUDY COMPLETION
	Visit 1	Visit 2	Visit 3	Visit 1	Visit 2	Visit 1	Visit 2	
Informed Consent	X							
Anthropometrics								
Weight	X			X	X	X	X	X
Height	X							
Vital Signs								
Blood Pressure	X			X	X	X	X	X
Heart Rate (Pulse)	X			X	X	X	X	X
Respirations	X			X	X	X	X	X
Temperature	X			X	X	X	X	X
Medical Evaluation								
Medical History	X							
Physical Examination	X							X
12-Lead Electrocardiogram	X							
Depression Screening	X					X		X
Lab/Blood Work								
Urine pregnancy test (females only)	X	X	X	X	X	X	X	
Urine drug test	X	X	X	X	X	X	X	
PT/INR	X							
CBC/diff	X					X		
CMP	X					X		
Lipid panel	X					X		
HbA1C	X					X		
Body composition analysis								
Dual energy X-ray absorptiometry (DXA)				X				
Abdominal MRI			X			X		
Liver volume, TG content and stiffness by MRI/MRE			X			X		
Metabolic function								
Modified 3-hour oral glucose tolerance test (mOGTT)				X		X		
Hyperinsulinemic-euglycemic clamp (HEC)					X		X	
Vision Testing								
Peripheral Vision Tests			X				X	X

Statistical Analyses

Statistical Analysis: The effect size of vigabatrin treatment on insulin sensitivity during the HEC and insulin secretion assessed during the mOGTT will be determined by using Cohen's d tests. Using these effects sizes we used G*Power 3.1.9.2 to estimate the number of participants per group that would be required to detect an ~15% improvement in insulin sensitivity between placebo and vigabatrin groups with >90% power using two-sided tests at the $\alpha=0.05$ level if a randomized, controlled trial were to be conducted.

PROTECTION OF HUMAN SUBJECTS

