This research involves collection of blood samples, each of which has potential risks associated. Possible side effects of venous catheter insertion are discomfort, bruising, bleeding, and/or infection at the site of needle insertion. Occasionally some people experience dizziness or feel faint. A blood clot can occur at the site of the arterial catheter insertion which could decrease blood flow to the hand and cause tissue damage requiring corrective surgery. However, the risk of this is extremely small because a small size catheter is used. Furthermore, before catheter placement, all subjects are examined to make sure that they have adequate blood flow to the hand from the other major artery that supplies the hand. Subjects who are judged to have insufficient compensatory blood flow will be excluded from the study. Lastly, there is a possibility that potentially adverse medical conditions will be identified as a result of the medical evaluation at screening.

Vigabatrin limits central nervous system GABA breakdown. Study subjects will be advised to not drive a car or operate other complex machinery until they are familiar with the effects of the study drug on their ability to perform these activities. Participants will be warned about possible complications and told to contact their physician and the study physician should they experience any of the side effects listed for vigabatrin (e.g. headache, irritability, dizziness, drowsiness, tiredness, memory problems, intrameylinic edema, weight gain, anemia, swelling, numbness/burning pain/tingly feeling in the hands or feet, loss of coordination, joint pain, cold symptoms (such as stuffy nose, fever, sneezing, sore throat), nausea, vomiting, diarrhea, sleep problems (insomnia), uncontrolled back and forth eye movements, tremors, pale skin, lightheadedness, shortness of breath, rapid heart rate, trouble concentrating, confusion, mood or behavior changes, depression, or thoughts about suicide). Participants will be given a list with suicide prevention resources at the time of Consent.

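### The protocol claims that participants and staff are blinded to treatment, but the trial has one arm and everyone knowingly receives vigabatrin

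*Combined protocol and SAP*

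**What the plan says.** The blinding claim appears once, in the Overview under Experimental Design: "Throughout the study, participants and the study team will be blinded to treatments". The protocol does not say what is masked, from whom, or how.

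The rest of the protocol describes an open study of one known drug:

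- **Specific Aims:** "we will conduct a 3-week, single-arm trial to assess the effect size of treatment with vigabatrin".
- **Overview**, in the same paragraph as the blinding sentence: "After completion of baseline testing, subjects will receive vigabatrin to be taken over 30 days". The sentence directly after the blinding claim describes participants stepping down their vigabatrin dose.
- **Intervention:** "we will provide each patient with a total dosage of 44.5 g vigabatrin", with the pill strength and the number of pills per day set out for each period. The drug is used as the manufacturer supplies it.
- **Dispensing and accountability:** "A medication accountability log will be used to document dispensing of the vigabatrin to the participant", and "The study research coordinator will perform a pill count and document this in the medication accountability log at each study visit".
- **Potential Risks:** participants are told to contact their own physician and the study physician "should they experience any of the side effects listed for vigabatrin".
- **Statistical Analyses:** a placebo group is mentioned only for a possible later randomised trial, which would be sized to detect an "improvement in insulin sensitivity between placebo and vigabatrin groups".

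**The concern.** Blinding to treatment means concealing which of at least two treatments a person receives. With one arm and one named drug there is nothing to conceal, so the sentence contradicts the design around it.

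This matters because the main product of the study is a pair of before/after effect sizes: insulin sensitivity during the clamp and insulin secretion during the oral glucose tolerance test. The Specific Aims and the background Summary tie the study to whether a larger randomised trial is warranted, and Statistical Analyses uses the effect sizes to plan a placebo-controlled comparison. In a study without a concurrent control, blinding would be one of the few protections a reader could credit to those estimates. An ethics reviewer, a safety board member or the planner of the next trial who takes the sentence at face value is misinformed about a basic design feature.

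Exposure to expectation differs by measure:

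- **More exposed:** participant-reported measures, that is the Beck Depression Inventory-II and adverse events.
- **Less exposed:** the Aim 1 and Aim 2 endpoints, because they rest largely on laboratory assays. They are not wholly automatic: glucose Rd includes the exogenous glucose infusion rate, which staff adjust during the clamp knowing whether the visit is before or after treatment. The glucose target and the checks every 10 minutes limit their discretion.

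**Working it through.** **Step 1. Is there more than one treatment?** Specific Aims: single-arm. Study Participants: 6 adults, with no allocation ratio. Intervention: the vigabatrin supply is stated for each patient. No randomisation is described. Number of treatments: one.

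**Step 2. Could some of the pills, or some period, be masked?** This can be checked against the protocol's own total. The inputs are the schedule and the 44.5 g per patient, both in the Intervention section; Potential Risks repeats the total. For each period, pills = days × pills per day, and grams = pills × 0.5.

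| Days | Number of days | Pills per day | Pills | Grams |
|---|---|---|---|---|
| 0–6 | 7 | 2 | 14 | 7.0 |
| 7–13 | 7 | 3 | 21 | 10.5 |
| 14–23 | 10 | 4 | 40 | 20.0 |
| 24–30 | 7 | 2 | 14 | 7.0 |
| Total | 31 | | 89 | 44.5 |

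Scheduled 44.5 g − supplied 44.5 g = 0 g. The stated total is reproduced only if all 89 scheduled pills are active drug. Placebo pills or a placebo period within a participant's schedule would break the match.

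(Days 0–30 make 31 dosing days, while the text gives 30 days. Those statements need reconciling, but the point has no bearing on blinding.)

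**Step 3. Is any masking procedure described?** No matching product, coded dispensing, unblinded pharmacist or code-break procedure is described. The accountability log names vigabatrin, the coordinator counts the pills, and participants are warned about that drug's side effects. Placebo is mentioned only for the possible future trial (Statistical Analyses) and for an outside trial in cocaine addiction (Potential Risks).

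**Step 4. Is there another reading that saves the sentence?** The one kind of masking this design could support is to hide visit order, before or after treatment, from assay staff or image readers. The documents do not describe it. The sentence speaks of participants and the study team, and of treatments. Participants cannot be masked to whether they have started the drug.

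**The case against.** The contradiction itself is hard to dispute. The case on the other side concerns its weight.

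1. **Few readers would be misled.** The Specific Aims say single-arm, and the sentences around the blinding claim name the drug. This is fair, and it limits the practical harm. It does not make the sentence correct, and the sentence stands in the operative design section, not in background text.

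2. **The measures most exposed to expectation do not feed the effect sizes.** Cohen's d is planned only for the clamp and glucose-tolerance outcomes, not for depression scores or adverse events. This stands. The main limit on those effect sizes is the lack of a concurrent control, which the protocol discloses and which correcting the sentence does not change.

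3. **The pill count proves less than it seems to.** The active arm of a two-arm trial would give the same 89 pills and 44.5 g. This also stands: the arithmetic excludes placebo within a participant's schedule, not a placebo arm. A placebo arm is excluded by the single-arm statement and by the supply being stated for each patient. The conclusion needs both parts.

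4. **Correcting the sentence changes no analysis, sample size or endpoint definition.** True. The point is about accurate description, and masking the laboratory to visit order would be an addition that the contradiction does not require.

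**Conclusion.** The concern holds. The stated blinding does not exist: 6 of 6 participants are to receive known vigabatrin, and 89 of 89 scheduled pills per participant are active. These counts describe the design; they do not measure bias, whose size cannot be derived from the documents.

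No planned analysis formally depends on blinding, and the endpoints used for the effect sizes are the less exposed ones. The sentence should still be corrected, because a protocol should not claim a protection it lacks when its estimates are meant to support the decision on a randomised trial and to size it.

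The conclusion assumes that the single-arm description and the per-patient supply state what is actually planned. If some narrower masking is intended, the protocol must say who is masked and to what.

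**What to change.** **Required**

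- In the Overview, replace the blinding sentence with: *The study is single-arm and open-label (unblinded); participants and study staff know that all participants receive vigabatrin.*
- In Statistical Analyses, describe the Cohen's d values as uncontrolled, unblinded before/after change, including where they are used to plan a future randomised trial.

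The cost is one replaced sentence and one added phrase, and a less favourable description of the trial. No dose, schedule, endpoint or calculation changes.

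**Optional, and separate from the correction**

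- Label stored plasma samples for the glucose, insulin, C-peptide and tracer assays with a code that hides the visit from laboratory staff. Samples already carry a subject number (Confidentiality), so this adds only minor bookkeeping.
- Do not extend this to real-time glucose monitoring during the clamp, the eligibility MRI or the safety reading of the vision tests, which need immediate results or knowledge of visit order.

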initiation with a two-step priming dose: 200 mU/m² BSA/min for 5 min followed by 100 mU/m² BSA/min for 5 min. This will result in plasma insulin concentrations of ~100 mU·L⁻¹. Dextrose, enriched with [6,6,-²H₂]glucose, to minimize changes in plasma glucose isotopic enrichment³⁴, will be infused at a variable rate to maintain plasma glucose concentration (monitored every 10 min) at ~100 mg/dl during insulin infusion. The [6,6,-²H₂]glucose infusion will be stopped during the clamp because of the expected decrease in hepatic glucose production³⁵. The insulin concentration achieved during the clamp reflects postprandial plasma insulin concentrations^{36,37} and is ideal to evaluate insulin's effect on glucose disposal³⁸. Blood samples for kinetic analyses will be collected immediately before the start of the tracer infusions and then every 6-7 min for a 20 min period at the end of the basal and insulin infusion stages. The data (average values) obtained during these times will be used to determine hormone and substrate concentrations and glucose enrichments to calculate the glucose rate of appearance (Ra) and disappearance (Rd) from plasma. Endogenous glucose rate of appearance (Ra) in plasma will be calculated by dividing the glucose tracer infusion rate by the average plasma glucose TTR during the last 20 min of the basal stage and at the end of the HEC procedure. Glucose Rd will be calculated as the sum of endogenous glucose Ra and the infusion rate of exogenous glucose. Insulin-induced stimulation of glucose Rd during the HEC procedure will be used as an index of skeletal muscle insulin sensitivity^{39,40}.

Sample processing

Plasma glucose concentration will be determined by using a YSI analyzer (Yellow Springs Instruments Co., Yellow Springs, OH) and plasma C-peptide and insulin concentrations will be determined by using electrochemiluminescence assays (Elecsys 2010, Roche Diagnostics, Indianapolis, IN). Plasma FFA concentrations will be assessed by gas chromatography⁴¹. Glucose tracer-to-tracee ratio in plasma will be measured by using gas-chromatography/mass-spectrometry as previously described⁴¹⁻⁴⁵.

Intervention

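### The single formula for endogenous glucose Ra holds at the basal stage but not in the clamp, so clamp Rd and its stimulation over basal are wrong as written

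*Combined protocol and SAP*

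**What the plan says.** The combined protocol and SAP describes the clamp under Baseline Testing Visit 2, in the paragraph on the hyperinsulinemic-euglycemic clamp (HEC). It gives one rule for endogenous production: "Endogenous glucose rate of appearance (Ra) in plasma will be calculated by dividing the glucose tracer infusion rate by the average plasma glucose TTR". The rule is to be applied "during the last 20 min of the basal stage and at the end of the HEC procedure". The next step is "Glucose Rd will be calculated as the sum of endogenous glucose Ra and the infusion rate of exogenous glucose".

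The same paragraph says how tracer reaches plasma in the clamp. The variable infusion is "Dextrose, enriched with [6,6,-²H₂]glucose, to minimize changes in plasma glucose isotopic enrichment", and the separate constant tracer "infusion will be stopped during the clamp because of the expected decrease in hepatic glucose production".

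The result serves Aim 1: "Insulin-induced stimulation of glucose Rd during the HEC procedure will be used as an index of skeletal muscle insulin sensitivity". The Statistical Analyses section takes "The effect size of vigabatrin treatment on insulin sensitivity during the HEC" as a Cohen's d and uses it to size a possible randomized trial for an improvement of about 15%. No other section gives a clamp-stage equation for endogenous Ra.

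**The concern.** Tracer rate divided by TTR estimates the appearance of all unlabelled glucose. At the basal stage that glucose is all endogenous, so the rule works. In the clamp most of it is infused dextrose, and the rule has no term to remove it. The text also leaves open which tracer rate is meant once the constant infusion has stopped. There are three readings:

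- **(a)** The stopped infusion, so the rate is 0. Endogenous Ra is then 0 and Rd equals the dextrose rate. This is right only if endogenous production is fully suppressed, and the plan speaks only of an expected decrease.
- **(b)** The tracer carried in the dextrose. The quotient then already contains the unlabelled dextrose, and the Rd step adds dextrose again.
- **(c)** The basal tracer rate carried forward. Enriching the dextrose is meant "to minimize changes in plasma glucose isotopic enrichment", so TTR stays near its basal value and the quotient returns about the basal Ra, as if nothing had been suppressed.

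At stake is the Aim 1 index. Basal Rd is right and clamp Rd is not, so the error does not cancel from the absolute value or from stimulation over basal. If residual endogenous production shifts between visits, part of a hepatic change would be read as a muscle effect.

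**Working it through.** The plan states no Ra, Rd or standard deviation, so there is no figure of its own to reproduce. The formulas come from the HEC paragraph. **All kinetic values below are assumptions**, in umol/kg FFM/min: total dextrose rate G = 25 to 45, residual endogenous production in the clamp E = 2 to 6, basal Ra = 12 to 18. Central values are G = 35, E = 4, basal Ra = 15. Steady state is assumed.

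**1. Mass balance.** Let F be the tracer rate and U the unlabelled dextrose rate. Plasma TTR = F/(E + U), so F/TTR = E + U. At baseline U = 0 and F/TTR = E, which is correct. In the clamp U > 0 and F/TTR exceeds E by U. True clamp Rd = E + G.

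**2. Clamp Rd as written** (tracer mass neglected in (b), so U is about G).

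| Reading | Rd as written | Ratio to true, range | Central Rd (true 39) | Stimulation over basal (true 39/15 − 1 = 160%) |
|---|---|---|---|---|
| (a) | G | 25/31 = 0.81 to 45/47 = 0.96 | 35 | 35/15 − 1 = 133% |
| (b) | 2G + E | 56/31 = 1.81 to 92/47 = 1.96 | 74 | 74/15 − 1 = 393% |
| (c) | basal Ra + G | 57/51 = 1.12 to 43/27 = 1.59 | 50 | 50/15 − 1 = 233% |

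With a dextrose TTR of 0.025, the range under (b) is 1.79 to 1.93.

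**3. A true 15% rise in clamp Rd, E fixed.**
- Clamp Rd under (a): 0.15(G + E)/G, which gives 15.7% to 18.6%.
- Clamp Rd under (b): 0.30(G + E)/(2G + E), which gives 15.3% to 16.6%.
- Percent stimulation at central values (Rd 39 to 44.85, a rise of 5.85): the true relative rise is 29.85/24 − 1 = 24%. Under (a) it is 25.85/20 − 1 = 29%, under (b) 70.7/59 − 1 = 20%, and under (c) 40.85/35 − 1 = 17%.

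**4. Paired Cohen's d on clamp Rd** (assumed mean change 5.85, SD of change 6).
- E fixed: the change under (a) equals the true change, and under (b) it is twice the true change with twice the SD. So d = 5.85/6 = 0.975 in all three cases.
- E changing at random between visits, independently of Rd, with SD of change 2: under (a) d = 5.85/sqrt(36 + 4) = 0.925, and under (b) d = 11.7/sqrt(144 + 4) = 0.962.

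**5. No muscle effect, but E changes.** Hold Rd at 39. If E goes from 4 to 2, G goes from 35 to 37: (a) reports +5.7% (37/35) and (b) +2.7% (76/74). If E goes from 4 to 6, they report −5.7% and −2.7%.

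**6. Check of the corrected equation.** Total dextrose 35 at TTR 0.025 gives U = 35/1.025 = 34.15 and F = 0.854. With E = 4, plasma TTR = 0.854/38.15 = 0.02238. Then F/TTR − U = 38.15 − 34.15 = 4.00 and Rd = 4 + 35 = 39.00, as it should be.

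**The case against.** The strongest reply is that this is a condensed methods paragraph and not evidence of wrong results. The paper cited for the enriched dextrose is, by its title, about estimating endogenous production during clamps, so the laboratory may well use the right equation. Reading (c) carries forward an infusion that the plan says is stopped. Reading (b) puts exogenous glucose into a quantity labelled endogenous. Reading (a) gives the smallest error, and none at all if E is 0. In a single-arm pilot of 6 the planned measure is Cohen's d. Its approximate standard error near d = 1 is sqrt(1/6 + 1/12) = 0.5, so the shifts in step 4 (at most 0.05) are about a tenth of that.

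Much of this stands as a limit on the harm. The documents do not show what the calculation sheet does, and they predict neither a change in E nor its direction. It does not make the rule right. The citation is attached to the enrichment and not to the Ra sentence, and no reading gives correct clamp Rd in general. The d argument concerns clamp Rd alone, whereas the named index is stimulation of Rd, with absolute or percent left unstated. For percent stimulation, step 3 shows that the before/after change moves in different directions under different readings.

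A smaller point also stands: the plan does not say how tracer mass is treated in basal Rd.

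**Conclusion.** The concern holds. Followed literally, the rule is right at the basal stage and wrong in the clamp, except under reading (a) with complete suppression of endogenous production. The size depends on the reading: clamp Rd 4% to 19% too low, nearly doubled, or 12% to 59% too high over the assumed ranges. The stated identity for Rd is sound; what is missing is a clamp-stage equation for endogenous Ra.

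The consequence is serious for absolute clamp Rd and for stimulation over basal. It is limited for the before/after result on clamp Rd: with E the same at both visits, d is unchanged under (a) and (b), and a percent change is only modestly inflated. The distortion grows if E changes or varies between visits. The algebra needs only steady state, but every magnitude rests on kinetic values that the documents do not supply. Because the rule defines the Aim 1 index, it must be corrected before that index is reported.

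**What to change.** Replace the single rule with separate equations.

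- **Basal:** endogenous Ra = tracer infusion rate / TTR.
- **Clamp:** F = rate of tracer delivered in the dextrose, from the dextrose infusion rate and bag enrichment over the sampling window. Endogenous Ra = F/TTR − unlabelled dextrose infusion rate. Rd = endogenous Ra + total (labelled plus unlabelled) dextrose infusion rate, counted once.

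State whether stimulation of Rd is absolute or percent over basal, and treat tracer mass in the same way at both stages. Check the calculation sheet against these equations; the worked check above can serve as a test case.

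The cost is protocol wording and a review of the sheet. No new samples or procedures are needed, and any affected value can be recalculated from the same infusion rates and TTRs.
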